6.2.11 End of Treatment Visit (Visit 15)

Subjects will complete the treatment at 12 ± 1 month following administration of loading dose and return to the study site for their final, End of Treatment Visit (Visit 15). Participants who choose to discontinue or who are withdrawn from the study will complete an Early Termination Visit (**Section 6.7**). It is highly encouraged that this visit occurs at the study site, but at the physician's discretion, this visit may occur remotely and subject may visit their local medical provider or facility (e.g. Quest Diagnostics). The below procedures will be conducted as standard of care:

- Physical exam including performance score (if visit occurs on site)
- Vital signs (if visit occurs on site)
- Radiological imaging (PET/CT or CT)
- Standard of Care Laboratory Tests (Appendix 15.4)
- Lipid panel
- Review of medication changes and updates

The below non-standard of care procedures will be conducted as part of this study during Visit 15:

- Research blood draw
- Pregnancy testing for females of childbearing potential (may be self-administered by subjects if visit is conducted remotely)
- Sirolimus Trough
- Assess possible AEs
- Return of any non-consumed sirolimus
- Sirolimus pill count (if visit occurs on site)
- Final assessment of primary objective
- Recording of medical history data, medication changes, AEs, and Laboratory Test, as available, (Appendix 15.4) from medical records into eCRF

6.3 Follow Up Phase of the Study

6.3.1 Visit 16

The subject will be contacted by phone 12 weeks \pm 2 weeks after the End of Treatment Visit or Early Termination Visit and asked questions regarding their health status, if they have become pregnant (if applicable), and if they have continued on drug off-study.

6.4 Rescue Therapy

At the discretion of the licensed site investigator, a subject can be removed from the trial due to disease progression or serious AE (SAE). Decision to remove a subject from the trial and which rescue therapy(ies) to administer rest solely with the licensed site investigator.

6.5 Unscheduled Visits

An unscheduled visit may be required to repeat a laboratory assay or to conduct further safety evaluation. Enrollment into this study places no restrictions upon subjects' ability to visit their physician outside of the study's scheduled visits. Health data generated from such visits will be incorporated into the eCRF at the time of the subject's next scheduled visit.

6.6 Subject Withdrawal

The criteria for enrollment must be followed explicitly. If a subject who does not meet enrollment criteria is inadvertently enrolled, that subject should be discontinued from the study. A subject may voluntarily discontinue participation in this study at any time without impact to their care. The licensed site investigator or Lead Principal Investigator may also, at his or her discretion, discontinue the subject from participating in this study at any time. If a subject is prematurely discontinued from participation in the study for any reason, at any time, at either the licensed site investigator's discretion or the subject's request, an effort must be made to document the reason(s) why a subject failed to return to the study site for necessary visits or is discontinued from the study. Subjects withdrawn from the study may be replaced at the Lead Principal Investigator's discretion. The primary reason for discontinuing participation in the study must be stated in the CRF and may include, but is not limited to, one of the following:

- Progressive disease as determined by the licensed site investigator
- Use of unapproved concomitant medications including any systemic therapy(ies) intended to treat iMCD, as described in the eligibility criteria
- Occurrence of intolerable AEs
- Withdrawal of consent by subject
- Noncompliance with protocol, e.g., the subject fails to appear at one or more visits
- Development of an intercurrent illness, injury, or medical condition likely to interfere with subject safety, the overall assessment, or the required administration of study medication
- Pregnancy
- Development of any condition for which the licensed site investigator feels treatment withdrawal is justified
- Termination of the study

6.6.1 Data Collection and Follow-up for Withdrawn Subjects

Subjects who withdraw consent to participate in the study will be seen for one final Early Termination Visit.

6.7 Early Termination Visit

Subjects who discontinue or are withdrawn early from the study will return to the study site for a final Early Termination Visit. Unless conducted as standard of care, the below standard of care procedures will be performed:

- Physical exam including performance score
- Vital signs

- Standard of Care Laboratory Tests (Appendix 15.4)
- Review of medication changes and updates

The below non-standard of care procedures will be conducted as part of this study during the Early Termination Visit:

- Research blood draw
- Assess possible AEs
- Return of any non-consumed sirolimus
- Sirolimus pill count
- Recording of medical history data, medication changes, AEs, and Laboratory Test, as available, (Appendix 15.4) from medical records into eCRF

7 Study Evaluations and Measurements

7.1 Medical Record Review

Variables to be abstracted from medical charts (paper or electronic) and entered in the eCRF include elements that fall under the below categories, as available through routine clinical practice or obtained as part of this study.

- Contact information and socio-demographics
- Diagnoses and anthropometric
- Physical exam
- Vital signs
- Pathology
- Laboratory
- Clinical Features
- Radiographic
- Co-morbid conditions
- Medications (previous and current)
- Adverse events
- End of study information (including information on early withdrawal)

7.2 Physical Examination

Physical examination will follow standard of care for the treatment of iMCD as well as those required for assessing the Study Endpoints. Information may be obtained from the medical record.

7.3 Vital Signs

Vital signs will be assessed during each visit in line with standard of care for the treatment of iMCD. Body temperature will be assessed with a digital thermometer under the tongue or in the axilla. Pulse oximetry will be assessed digitally. Blood pressure and pulse rate will be assessed using a digitally-read cuff on individuals sitting up. Respiration rate will be determined by a medical professional.

7.4 Laboratory Evaluations

Blood sampling will be performed for this study for the following laboratory evaluations. Other laboratory tests will be collected as part of standard of care treatment and recorded in the eCRF from medical record review.

- Sirolimus trough levels
- Pregnancy testing (if applicable)
- Lipid panel (if not collected as standard of care)

7.4.1 Clinical Laboratory Tests

Appendix 15.4 contains a listing of standard of care labs that will be collected from subjects' medical records and recorded into the eCRF as part of this study.

7.5 Pregnancy Testing

Women of childbearing potential must have a negative pregnancy test documented during the Baseline Visit. Urine pregnancy testing will be conducted at each on-site visit. If a follow-up visit is conducted remotely, a subject may perform the pregnancy test at home and provide results to the study team via photo.

7.6 Efficacy Evaluations

The below measures will be used to assess the efficacy of the study intervention and determine if the subject meets criteria for a CBR. All comparisons are against those obtained during the Baseline Visit:

Positive response: Relative to baseline, improvement in at least one of the below criterion without worsening of any single criterion other than hemoglobin on two consecutive study visits.

Negative response: Relative to baseline, worsening of any single criterion other than hemoglobin on two consecutive site visits or failure to achieve improvement for any criterion.

	Hemoglobin	Fatigue	Anorexia	Fever and night sweats	Weight	Lymph node size
Improvement	≥2 g/dL increase without transfusions	≥1 grade decrease by NCI CTCAE version 4.0, May, 2009	≥1 grade decrease by NCI CTCAE version 4.0, May, 2009	≥2°C decrease in fever or return to normal body temperature (37°C) or improvement in night sweats, as assessed by licensed site investigator	≥5% increase not due to increase in new or existing edema	≥25% decrease bi-dimensionally in size of largest lymph node, as measured using Cheson criteria (Appendix 15.2)
Worsening		≥2 grade increase by NCI CTCAE version 4.0, May, 2009	≥2 grade increase by NCI CTCAE version 4.0, May, 2009	≥2°C increase in fever or worsening in night sweats, as assessed by licensed site investigator	≥5% decrease (weight loss not due to decreased edema)	≥25% increase bidimensionally in size of largest lymph node, as measured using Cheson criteria (Appendix 15.2)

The below table provides the CHAP score, which will be used to assess the efficacy of the study intervention. All comparisons are against those obtained during the Baseline Visit:

Score:	0	1	2	3	4
CRP (mg/dL)	<1	≥1, <5	≥5, <10	≥10, <20	≥20
Hemoglobin (g/dL)	≥12	<12, ≥10	<10,≥8	<8	Transfusion dependent
Albumin (g/dL)	≥3	<3,≥2.5	<2.5, ≥2	<2, ≥1.5	<1.5
Performance Score (ECOG)	0	1	2	3	4

The below table provides the modified Cheson response criteria, which will be used to assess the efficacy of the study intervention. Unless otherwise specified, all comparisons are against those obtained during the Baseline Visit:

Complete Response (CR)	All index lesion(s) must have regressed to normal size (≤1.0 cm in		
	their greatest transverse diameter. No new sites of		
	lymphadenopathy >1.5 cm in longest dimension.		
Partial Response (PR)	≥50% decrease in sum of the products of the greatest diameters		
	(SPD) of index lesion(s), and no new sites of lymphadenopathy >1.5		
	cm in longest dimension.		
Stable Disease (SD)	Failure to achieve a CR or PR (see above) without evidence of		
	progressive disease (see below).		
Progressive Disease (PD)	≥50% increase from nadir in the SPD of any index lesion, or		
	appearance of any new sites of lymphadenopathy that measure >1.5		
	cm in longest dimension during or at the end of therapy.		

MCD-related Overall Symptom Score: In addition to the defined CBR, 34 measures of disease activity will be prospectively evaluated and graded (as per CTCAE version 4.0, May, 2009), which will be used to assess the efficacy of the study intervention. All comparisons are against those obtained during the Baseline Visit:

General MCD-related

- Fatigue
- Malaise
- Hyperhidrosis
- Night sweats
- Fever
- Weight loss
- Anorexia
- Tumor pain
- Dyspnea
- Pruritis

Autoimmune phenomena

- Autoimmune disorder
- Immune system disorder

Fluid retention

- Generalized edema
- Edema face
- Edema limbs
- Edema trunk
- Genital edema
- Localized edema
- Neck edema
- Periorbital edema
- Capillary leak syndrome

- Ascites
- Pleural effusion
- Pericardial effusion

Neuropathy

- Peripheral motor neuropathy
- Peripheral sensory neuropathy
- Nervous system disorder, other

Skin disorders

- Rash acneiform
- Rash maculo-papular
- Papulopustular rash
- Purpura
- Skin hyperpigmentation
- Skin induration
- Skin disorder, other

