3.2 Study Endpoints

3.2.1 Primary Study Endpoints

The primary endpoint of this study will be the proportion of patients achieving a positive CBR response (**Section 7.6**, **Efficacy Evaluations**) at 12 ± 1 month. Assessments at 12 ± 1 month will be compared to those obtained at the Baseline Visit.

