4.2 Exclusion Criteria

To be eligible, subjects must not violate any of the below exclusion criteria.

- 1. Subjects cannot be pregnant or nursing females
 - Women of childbearing potential must have a negative pregnancy test documented at the Baseline Visit. Subjects of reproductive potential may not participate unless they have agreed, as part of the informed consent, to use an effective contraceptive method for the duration of the study and for at least 12 weeks after ending treatment
- 2. Subjects cannot have received any systemic therapy(ies) intended to treat iMCD other than corticosteroids within 14 days of enrollment
 - Corticosteroid treatment must have been initiated more than 28 days prior to enrollment and be maintained at a stable or tapering dose (prednisone or equivalent up to 1 mg/kg/day) prior to enrollment; dose cannot be elevated for the duration of the study but can be maintained or tapered
 - For subjects who cannot or are unwilling to undergo a 14 day washout period:
 - i. Anti-IL-6 therapy may be permitted if the subject has been on therapy for at least 3 months, no toxicity has been documented, and sufficient disease control is not achieved
 - ii. Anti-IL-6 therapy must be discontinued within the first 6 weeks after starting sirolimus
- 3. Subjects cannot have previously received sirolimus monotherapy to treat iMCD

- 4. Subjects cannot have any of the following:
 - ECOG >3 (or Karnofsky/Lansky score ≤ 60 in children)
 - Estimated glomerular filtration rate (eGFR) < 30 mL/min/1.73 m² or creatinine > 3.0 mg/dL
 - Absolute neutrophil count (ANC) < 1000 x 10⁹/L (< 500 x 10⁹/L in children)
 - Hemoglobin ≤ 6.5 g/dL (transfusion independent, defined as not receiving a red blood cell transfusion for ≥ 7 days prior)
 - Aspartate aminotransferase (AST) or alanine aminotransferase (ALT) laboratory values greater than three times the upper limit of normal
 - Albumin < 2 g/dL (transfusion independent, defined as not receiving intravenous albumin for ≥ 7 days prior)
 - Platelet count $\leq 40 \times 10^9$ /L (transfusion independent, defined as not receiving platelet transfusion for ≥ 7 days prior)
 - Pulmonary involvement or interstitial pneumonitis with dyspnea (adequate pulmonary function is defined as pulse oximetry > 94% on room air if there is clinical indication for determination [e.g. dyspnea at rest, history of interstitial pneumonitis, etc.])
 - Fasting cholesterol > 300 mg/dL or fasting triglyceride > 400 mg/dL

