6.1 Screening Phase

6.1.1 Screening Visit (Visit 0)

Subjects' eligibility will be confirmed during the screening phase. The below standard of care procedures will be conducted unless they occurred within four weeks prior to the screening visit as part of standard of care treatment.

- Standard Diagnostic Laboratory Tests (Appendix 15.4)
- Vital signs
- Radiological imaging (PET/CT or CT)
- Lipid panel

Review of concomitant medications

The below non-standard of care procedures will be conducted as part of the screening phase for all subjects:

- Informed consent: a signed and dated Institutional Review Board (IRB) approved informed consent form (ICF) that will be documented in the subject's source documents
- Pregnancy testing for females of childbearing potential
- Recording of demographic information (gender, date of birth, race, etc.) into electronic case report form (eCRF)
- Recording of medical history data and Laboratory Tests, as available, (Appendix 15.4) from medical records into eCRF

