6.2 Intervention Phase

6.2.1 Baseline Visit (Visit 1)

The baseline visit should occur within 7 days of the screening visit, following confirmation of eligibility. The below standard of care procedures will be conducted unless they occurred within four weeks prior to Visit 0 as part of standard of care treatment.

- Physical exam including performance score
- Vital signs
- Lipid panel
- Review of concomitant medications

The below non-standard of care procedures will be conducted as part of Visit 1 for all subjects:

- Confirmation that subject meets inclusion criteria and does not violate any exclusion criteria, including confirmation by the Lead Principal Investigator
- GUID assigned
- Research blood draw
- Collection of fecal sample (optional)
- Recording of medical history data and Laboratory Tests, as available, (**Appendix 15.4**) from medical records into eCRF
- Dispensing of sirolimus loading dose (adults only)
- Dispensing of sirolimus daily dose

6.2.2 Visits 2 and 3

Subjects will visit the study center, or may visit their local medical provider or facility (e.g. Quest Diagnostics), 5 days \pm 2 days (Visit 2) and 2 weeks \pm 5 days (Visit 3) following administration of loading dose/first dose. The below non-standard of care procedures will be conducted as part of this study during Visits 2 and 3:

- Research blood draw
- Recording of medical history data and Laboratory Test, as available, (**Appendix 15.4**) from medical records into eCRF (at site)
- Phone assessment of AEs, study drug compliance, and review of medication changes
- Sirolimus Trough

Collection of fecal sample (optional – Visit 3 only)

6.2.3 Visit 4

Subjects will return to the study site 1 month \pm 1 week following administration of loading dose. At the physician's discretion, this visit may occur remotely and subject may visit their local medical provider or facility (e.g. Quest Diagnostics). The below procedures will be conducted as standard of care:

- Physical exam including performance score (if visit occurs on site)
- Vital signs (if visit occurs on site)
- Lipid panel
- Standard of Care Laboratory Tests (Appendix 15.4)
- Review of medication changes

The below non-standard of care procedures will be conducted as part of this study during Visit 4:

- Research blood draw
- Pregnancy testing for females of childbearing potential (may be self-administered by subjects if visit is conducted remotely)
- Sirolimus Trough
- Assess possible AEs

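### Response is judged against the Baseline Visit, but its hemoglobin, CRP, albumin and nodal reference values come from Screening or earlier and can have been taken on prior therapy

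*Combined protocol and SAP*

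**What the plan says.** Section 3.2.1 sets the reference for the primary endpoint: "Assessments at 12 ± 1 month will be compared to those obtained at the Baseline Visit". Section 7.6 says the same for the CBR and CHAP tables: "All comparisons are against those obtained during the Baseline Visit". The modified Cheson table in 7.6 also refers back to that visit unless it says otherwise, and section 8.1 repeats the rule for the primary analysis.

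Before treatment, the diagnostic laboratory tests (which include the blood count, CRP and albumin, per Appendix 15.4) and the PET/CT or CT scan are listed only at Screening, in section 6.1.1. They are to be done "unless they occurred within four weeks prior to the screening visit as part of standard of care treatment".

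Section 6.2.1 lists, for Visit 1, an examination with performance score, vital signs, a lipid panel, a medication review, a research blood draw and the transcription of whatever laboratory results are in the medical record. The standard-of-care items there are waived too: they are done "unless they occurred within four weeks prior to Visit 0 as part of standard of care treatment". The calendar in Appendix 15.3 agrees. It marks diagnostic laboratory tests and pre-treatment imaging only in the Screening column, and standard-of-care laboratory tests start at Visit 4.

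On timing, section 6.2.1 says: "The baseline visit should occur within 7 days of the screening visit, following confirmation of eligibility". Section 4.4 and the calendar allow up to 28 days for screening.

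On prior therapy, section 4.2 says: "Subjects cannot have received any systemic therapy(ies) intended to treat iMCD other than corticosteroids within 14 days of enrollment". Stable or tapering corticosteroids may continue. Subjects who cannot or will not wash out may, under conditions, stay on anti-IL-6 therapy into the first 6 weeks of sirolimus.

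**The concern.** The visit named as the reference has no scheduled measurement of its own for several components of the endpoints. The permitted substitutes can be older than the washout, so a site that follows the protocol exactly can record a reference value obtained while the subject was on another iMCD treatment.

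The effect can go either way. A hemoglobin lowered by prior treatment may rise once that treatment stops, and the rise would be credited to sirolimus. A hemoglobin or node partly controlled by prior treatment leaves less room for improvement and can hide a benefit.

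The design is sensitive to this. There is no control arm to carry the same bias. A positive CBR needs improvement in one criterion with no sustained worsening in the others, and hemoglobin has no worsening entry. A 2 g/dL recovery can therefore make a responder by itself if nothing else deteriorates. One response among the first 14 subjects is enough to pass the interim rule in section 8. At 24 evaluable subjects, one misclassified subject moves the response rate by 1/24 = 4.2 percentage points.

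**Working it through.** The plan states no figure for the age of a baseline value, so there is none to reproduce. The check sets the schedule against the endpoints and does day arithmetic on the stated windows.

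**1. Components without a scheduled Visit 1 measurement**
- CBR has six criteria: hemoglobin, fatigue, anorexia, fever and night sweats, weight, and node size. Hemoglobin and node size have none: 2 of 6.
- CHAP has four items: CRP, hemoglobin, albumin and ECOG. The first three have none: 3 of 4.
- The modified Cheson response depends wholly on imaging.
- Examination, performance score and vital signs are listed at Visit 1, but the waiver lets an older result stand in for them.

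**2. Overlap with prior therapy**
- Look-back for Screening laboratory tests and imaging: 28 days before Visit 0 (6.1.1).
- Washout: 14 days before enrollment (4.2). Enrollment is the signing of consent (3.1.1), and consent takes place at the Screening Visit (12.4), so both periods count back from the same visit.
- Days on which an accepted value may be on prior therapy = 28 − 14 = 14 of 28, that is, days 28 to 14 before consent.
- Under the anti-IL-6 exception there is no washout, so every pre-treatment value can be on therapy.

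**3. Maximum age of a value**
- At Visit 1, under the 7-day rule: 28 + 7 = 35 days.
- At first dose, if the 7-day rule and the calendar's Visit 1 window of −7 to 0 both apply: Screening is no earlier than day −(7 + 7) = −14, so the age is 28 + 14 = 42 days.
- At first dose, if the calendar's −28 to 0 Screening window overrides the 7-day rule: 28 + 28 = 56 days.

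**4. Is a baseline value defined elsewhere?**
Section 3.1.1 calls 6.1.1 the Baseline Visit, although 6.1.1 is headed as the Screening Visit. Section 4.4 speaks of a combined screening and baseline phase. The opening text of section 6 refers to the imaging modality and laboratory provider used at the Baseline Visit. No section states which pre-dose value is the baseline, how old it may be, or how it relates to the washout.

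**The case against.** The strongest reply is that this is a labelling gap. Screening values commonly serve as baseline. The cross-reference in 3.1.1, the combined phase in 4.4 and the transcription of available laboratory results at Visit 1 all point that way, and Appendix 15.2 speaks of index lesions chosen at baseline. Much of this stands: a reader might infer that the trial has no baseline hemoglobin or scan at all, and the documents do not support that. But adopting Screening values does not answer the point about therapy, because under the waiver the last pre-dose value may itself be the on-therapy one.

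Other stronger readings also fail:
- **Every efficacy endpoint is affected.** The two drug-continuation endpoints in 3.2.2 need no baseline, and Cheson progression by nodal size is measured from nadir.
- **Half of the subjects are affected.** The 14 of 28 is a share of calendar days. The overlap matters only where a site reuses an earlier result and the subject was then on systemic therapy, and the documents give no frequency for either.
- **Baselines may simply be 56 days old.** That figure breaks the 7-day rule in 6.2.1.
- **The bias is beyond examination.** Section 7.1 has previous and current medications, laboratory results and radiology abstracted. If dates are recorded, affected subjects can be identified and the influence of their values examined, although the missing measurement cannot be recovered.

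**Conclusion.** The point holds as a defect in how the reference value is scheduled and defined. A compliant baseline can be an on-therapy value for hemoglobin, node size, CRP and albumin: 2 of 6 CBR criteria, 3 of 4 CHAP items and the modified Cheson response. The exposed period is days 28 to 14 before consent, or all pre-treatment values for subjects under the anti-IL-6 exception. Values can be 35 days old at Visit 1 and 42 days old at first dose under the two rules that can hold together.

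This rests on consent being signed at the Screening Visit, as 12.4 says, and on the visit list and calendar being complete. Confidence is high on the scheduling gap. The direction of bias is not fixed, and its size cannot be estimated from the documents, so no claim is made that the response rate is inflated. The change should be made, but the design does not fail without it.

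**What to change.** 1. Add a blood count, CRP and albumin to Visit 1 before the first dose, alongside the blood draw already scheduled. Record weight, temperature and performance score there without the four-week waiver.
2. In 7.6 and 8.1, define baseline as the last value on or before first dose, name the Screening scan as the nodal baseline, and state a maximum age for each. Do not also require that the value follow the last prior therapy: subjects under the anti-IL-6 exception would then have no baseline, nor would those on continuing corticosteroids unless exempted.
3. Flag each subject whose baseline laboratory value or scan was taken on prior systemic iMCD therapy other than permitted corticosteroids, including the exception subjects. Keep them in the primary analysis and repeat it without them as a sensitivity analysis.
4. Reconcile the screening windows in 4.4, 6.2.1 and Appendix 15.3, and correct the cross-reference in 3.1.1.

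The cost is three routine assays per subject, a definition, and one further analysis on a set smaller than the at most 24 evaluable subjects. Two limits remain. Recovery from therapy stopped shortly before enrollment can still be credited to sirolimus, and the node criterion is flagged but not re-measured, since no extra scan is proposed.

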3.1.2 Intervention Phase

Adult subjects will receive an oral sirolimus loading dose of 5 mg/m², rounded to the nearest mg (day 1). Loading dose may be lower at the discretion of the prescribing physician. Starting on day 2, adult subjects will receive oral sirolimus daily at 2.5 mg/m²/day (rounded to the nearest mg), adjusted as needed to a target trough level of 10-15 ng/mL. Pediatric subjects will not receive a loading dose, and daily dosing will be at 2 mg/m²/day (rounded to the nearest mg), adjusted to achieve a target trough level of 5-15 ng/mL. Subjects will remain on treatment for 12 ± 1 month. The period between the loading dose/first dose and the last treatment define the "Intervention Phase". Patients will continue to receive standard of care treatment during the Intervention Phase consistent with the requirements of **Section 6.6, Subject Withdrawal**. Subjects will undergo regular Intervention Phase visits (**Section 6.2, Intervention Phase**). The licensed site investigator will be ultimately responsible for all treatment decisions, including when to initiate rescue therapy (**Section 6.4, Rescue Therapy**).

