7.10 Concomitant Therapies

Corticosteroids (stable dose) and best supportive care are allowed throughout the course of the Intervention Phase. No additional systemic therapies directed at treating iMCD are permitted during the Intervention Phase.

8 Statistical Plan

This trial is a Phase II study of the efficacy and mechanism of action of sirolimus in anti-IL-6 blockade refractory iMCD. The trial is designed to rule out a therapy that has little or no biological activity in the examined patient cohort, a treatment-refractory population. The minimal acceptable level of activity is $\geq 20\%$. A common dose and dosing schedule will be employed for all subjects. An interim analysis will be conducted after 14 subjects have completed the Visit 9 intermediate assessment. If no responses are observed in these first 14 subjects, then the probability(response probability $\geq 20\%$) < 0.05, and the trial should be terminated. If at least one response is observed, additional subjects may be enrolled to increase the degree of precision of the standard error, to a total of 24 evaluable subjects.

The statistical considerations for this study were developed to answer the two overall research questions:

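### Subjects withdrawn for progression or prohibited iMCD therapy most naturally fall out of the month-12 CBR rate instead of counting as failures; one rescued but kept on study could be scored positive

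*Combined protocol and SAP*

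**What the plan says.** **Scoring.** Section 7.6 defines a positive CBR as "improvement in at least one of the below criterion without worsening of any single criterion other than hemoglobin on two consecutive study visits", and a negative one as "worsening of any single criterion other than hemoglobin on two consecutive site visits or failure to achieve improvement for any criterion". All comparisons are with the Baseline Visit. Two outside influences are discounted: transfusion for hemoglobin, and edema for weight. Other iMCD therapy and steroid dose are not mentioned. Section 8.1 places the primary assessment at 12 ± 1 month and refers back to 7.6.

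**Conduct.** Section 7.10 states: "No additional systemic therapies directed at treating iMCD are permitted during the Intervention Phase". Section 4.2 says of corticosteroids that the "dose cannot be elevated for the duration of the study but can be maintained or tapered". Section 3.1.2 adds: "Patients will continue to receive standard of care treatment during the Intervention Phase consistent with the requirements of" Section 6.6. It also makes the site investigator "ultimately responsible for all treatment decisions, including when to initiate rescue therapy". Section 6.4 mentions rescue only alongside removal from the trial and leaves both to the site investigator. Section 6.6 lists possible reasons for discontinuation. Among them are progression as judged by the site investigator and "Use of unapproved concomitant medications including any systemic therapy(ies) intended to treat iMCD, as described in the eligibility criteria".

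**Analysis after withdrawal.** Section 6.6 lets the Lead Principal Investigator replace a withdrawn subject. Section 6.2.11 sends withdrawn subjects to the Early Termination Visit. Section 6.7 gives that visit an examination, vital signs and laboratory tests, but neither imaging nor an assessment of the primary objective. Section 8.6 counts every dosed subject in the analysis of each visit completed. Section 8.4 places replaced dropouts in the gap between 40 enrolled and 24 evaluable. The documents do not define evaluable.

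**The concern.** The rules on prohibited therapy govern conduct. None of them says how CBR is scored once therapy has been added, the steroid dose raised, or the subject removed for progression.

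That matters here because the trial is open-label with a single arm, and one improved criterion is enough for a response. Section 1.1 names corticosteroids among the treatments used for iMCD, so an improvement produced by them could be credited to sirolimus. A subject taken off sirolimus for progression has failed treatment, yet need not appear in the month-12 rate at all. The primary result then depends partly on discretionary choices to keep, remove or replace a subject.

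**Working it through.** **Inputs.** From the documents: up to 24 evaluable subjects (8.4); interim look after 14 subjects complete Visit 9, stopping if none responds (Section 8); minimal activity of 20% (Section 8). Assumed: 5 responders, and 1, 2 or 4 subjects withdrawn for progression or prohibited therapy. The documents give no rate of rescue, deviation or removal.

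**1. The plan's own figure.** The stopping rule reproduces: 0.8^13 = 0.055 and 0.8^14 = 0.044, so 14 is the smallest n at which no responses has probability below 0.05 when the true rate is 20%. Nothing below changes it.

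**2. Withdrawn subjects.** Such a subject goes to the Early Termination Visit (6.2.11) and does not complete Visit 15. Section 8.6 counts subjects only at visits they complete, so the natural reading is a month-12 analysis of available cases. If the subject is replaced, 8.4 leaves the original subject outside the evaluable 24. The subject still counts at earlier completed visits, and as not remaining on drug, a secondary endpoint (3.2.2).

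**3. Effect on the rate, 5 responders assumed.** Counted as failures, the rate is 5/24 = 20.8%. Left out and not replaced, it is 5/(24 − r):

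| r left out | Rate |
|---|---|
| 1 | 5/23 = 21.7% |
| 2 | 5/22 = 22.7% |
| 4 | 5/20 = 25.0% |

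If they are replaced, 5/24 = 20.8% is reported, while the rate among all treated subjects is 5/(24 + r):

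| r replaced | Rate among treated |
|---|---|
| 1 | 5/25 = 20.0% |
| 2 | 5/26 = 19.2% |
| 4 | 5/28 = 17.9% |

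**4. Subjects kept on study.** Suppose the steroid dose is raised mid-study and at Visit 15 the subject is one fatigue grade better than baseline, with no other criterion worse. Section 7.6 scores this positive. A flare before the increase can be recorded, through the phone reviews or unscheduled visits (6.5). It makes the subject negative only if a criterion other than hemoglobin crosses its worsening threshold on two consecutive visits. Each such subject adds 1/24 = 4.2 points: 6/24 = 25.0% against 5/24 = 20.8%.

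**5. Sampling error.** The exact (Clopper-Pearson) 95% limits for 5/24 are the 2.5% point of Beta(5, 20) and the 97.5% point of Beta(6, 19), which give 7.1% and 42.2%. Every shift above lies inside that interval.

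**6. Interim gate.** One response in 14 is enough to allow continuation. A wrongly credited response changes the outcome only if none of the 14 is a genuine responder. Continuation is also a judgement and not automatic (8.5.2).

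**The case against.** **The status is already settled.** A reader might infer that the plan simply leaves the withdrawn subject's status blank. That goes too far: 8.6 is a terse available-case rule, and this point is largely a preference for counting failures as failures. That much stands. The negative definition in 7.6, which covers failure to improve, could be read the other way. The two readings give different rates, so the choice should be written down.

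**Retention after rescue is a violation.** A reader might infer that the plan provides for rescue while staying on study. It does not: 4.2 and 7.10 forbid the therapy, and 6.4 mentions rescue only with removal. What remains is that removal is discretionary and 8.6 keeps the retained subject in the analysis. This route is a deviation of unknown frequency and the lesser part of the point.

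**The 20% level.** A reader might infer from 5/26 = 19.2% that a few subjects could decide the trial. No section applies 20% to the final estimate. Section 8.5.1 plans a confidence interval and a chi-square test against historic placebo data. The crossing also depends on assuming 5 responders: 4/24 = 16.7% starts below 20%, and 6/28 = 21.4% stays above it. Nor can the surplus of 40 − 24 = 16 enrollees be read as 16 discarded failures, because 8.4 says that it includes subjects found ineligible at screening.

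**Direction.** That the rate can only be equal or higher follows from the chosen comparison, in which these subjects are failures. If a removed subject had in fact improved on sirolimus, omission lowers the rate relative to observed response. This is correct, and it is why the comparison is stated each time.

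**Adjudication.** Section 9.7.2 says the DSMB may adjudicate final outcome. It is optional, and the charter is not among the documents, so it cannot be relied on as the missing rule.

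**Conclusion.** The point holds as a cheap improvement. The main problem is that dosed subjects withdrawn for progression or prohibited iMCD therapy most naturally leave the month-12 CBR denominator. The lesser one is that a subject rescued and kept on study, contrary to protocol, can be scored positive. Relative to counting both as failures, the primary rate is equal or higher.

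The actual bias is unknown, since it depends on event counts the documents do not give. In the illustration, omission adds 0.9 to 4.2 points (21.7% − 20.8% to 25.0% − 20.8%), and replacing 2 subjects overstates the rate among treated subjects by 1.6 points (20.8% − 19.2%). These shifts are small beside the sampling error, and the calculations show no changed final conclusion. Withdrawal for other reasons is outside this point.

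**What to change.** Leave the clinical rules as they are and add to Sections 7.6, 8.1 and 8.6:

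> A dosed subject who, after the first sirolimus dose, receives other systemic iMCD-directed therapy (beyond the 6-week anti-IL-6 overlap in 4.2), or a corticosteroid dose for iMCD above the Baseline Visit dose, or who is withdrawn for disease progression or unapproved iMCD medication, is CBR negative at that and every later assessment and stays in the denominator, whether or not replaced.

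Report as-observed CBR as a sensitivity analysis. The steroid trigger is set at the Baseline Visit dose because CBR is measured from baseline. A subject who tapers and then steps up to a dose at or below baseline should not be failed.

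**Cost.** One sentence in three sections. Medication changes and the primary reason for discontinuation are already recorded; visits, sample size and patient care do not change. The reported rate may be somewhat lower, and a true responder given a brief steroid increase above baseline would count as a failure; the sensitivity analysis shows how much this matters. The rule still relies on the investigator's coded reason for withdrawal or steroid use, so discretion is reduced but not removed.
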